4.7. Treatment

4.7.1. Treatments to be given

According to section 4.7.1. of the accompanying master protocol:

Vaccines to be evaluated in sub-protocols under the master protocol will be vaccines with marketing authorization at the time of each sub-protocol design and/or vaccines still in clinical development, i.e., pre-authorisation. Vaccines to be administered in the intervention and control arms will be defined in each sub-protocol depending on the hypothesis and the booster strategies tested.

Subjects allocated to control arms could receive a 3rd vaccine dose or not receive a 3rd vaccine dose.

Specific to this trial, Part B:

Study vaccines will be given as a 4th dose in subjects already vaccinated with defined prior vaccination strategies (with BNT162b2, mRNA-1271 or ChAdOx-1-S) as per eligibility criteria. The

vaccines to be evaluated as 4th vaccination (second booster) dose will be BNT162b2 (Comirnaty®) and mRNA-1273 (Spikevax®). For a detailed overview of all cohorts and arms in this study please refer to Tables 2.1 and 2.2 below.

In Part B there is a minimum interval of 1 month between the on-study 4th vaccination dose and the 3rd pre-study vaccination, with longer intervals as per local regulation or practice.

Table 2.1: **Intervention in Part A** no longer active - for information only

Cohort	Vaccination prior to study entry	Arm	Study intervention: 3 rd vaccination dose	Part A with Cohorts 1 to 3 closed to further recruitment as of January 13, 2022
Cohort 1	BNT162b2 + BNT162b2	1	BNT162b2	
		2	mRNA-1273	
Cohort 2	mRNA-1273 + mRNA-1273	3	BNT162b2	
		4	mRNA-1273	
Cohort 3	ChAdOx-1-S + ChAdOx-1-S	5	BNT162b2	
		6	mRNA-1273	
Control	Control arm of the EU-COVAT subprotocol EudraCT no. 2021-004889-35, a separate sub-protocol embedded within the EU-COVAT master protocol, will be used for a descriptive comparison.			

Table 2.2: **Intervention in Part B - 4th vaccination dose**

Cohort	Vaccination prior to study entry	Arm	Study intervention: 4 th vaccination dose*
Cohort 4	BNT162b2 + BNT162b2 + BNT162b2	7	BNT162b2
		8	mRNA-1273
Cohort 5	BNT162b2 + BNT162b2 + mRNA-1273	9	BNT162b2
		10	mRNA-1273
Cohort 6	mRNA-1273 + mRNA-1273 + mRNA-1273	11	BNT162b2
		12	mRNA-1273
Cohort 7	mRNA-1273 + mRNA-1273 + BNT162b2	13	BNT162b2
		14	mRNA-1273
Cohort 8	ChAdOx-1-S + ChAdOx-1-S + BNT162b2	15	BNT162b2
		16	mRNA-1273
Cohort 9	ChAdOx-1-S + ChAdOx-1-S + mRNA-1273	17	BNT162b2
		18	mRNA-1273

* administered at least 1 month after the 3rd pre-study vaccination.

4.7.2. Description of investigational medicinal product

Trade name: Comirnaty®

INN (International Nonproprietary Name)/active substance:

COVID-19 mRNA vaccine(nucleoside-modified).

ATC-Code: J07BX

Presentation: vaccine shot for intramuscular injection.

Dose: 30 µg (0.3 mL after dilution).

Manufacturer (or marketing authorisation holder if applicable): Pfizer-BioNTech.

Already approved for the following indication: Protection against COVID-19 infection.

Please note: Can be modified in composition to address emerging VOCs.

Trade Name: Spikevax®

ATC-code: J07BX03

Presentation: Dilution, vaccine shot for intramuscular injection.

Dose: 100 µg (0.5 mL after dilution); **please note that the 50 µg (0.25 mL) dose is not used in this trial - see dose justification further down below.**

Manufacturer: Moderna.

Already approved for the following indication: Protection against COVID-19 infection.

Please note: Can be modified in composition to address emerging VOCs.

4.7.2.1. Manufacture of the investigational medicinal product

Not applicable.

4.7.2.2. Labelling of investigational medicinal product

Vaccines to be administered in this trial are already marketed. Therefore, labelling is carried out as approved in each country. Preparation of the dose of each vaccine will be done according to the respective SmPC.

4.7.3. Storage of investigational medicinal product

All study vaccines must be stored in a secured location with no access for unauthorised personnel and at controlled temperatures as indicated on the commercial labels and manufacturer instructions.

If study vaccine is exposed to temperatures outside the specified temperature range according to SmPC as per market authorization, then the affected supplies will be destroyed in line with locally regulated procedures and replaced with new supplies.

Instructions for the preparation, handling and storage will be those described in the SmPC of COMIRNATY and SPIKEVAX approved by Regulatory Authorities. The investigator is responsible for ensuring that all study vaccines received at the site is inventoried and accounted for throughout the study. The study vaccine administered to the participant must be documented on the vaccine (drug) accountability form. All study vaccine will be stored and disposed of according to the manufacturer's instructions. Destruction of vaccines will be recorded on appropriate drug destruction logs.

4.7.4. Compliance with treatment/Dispensing and return of investigational medicinal product

This study will be conducted within hospitals and/or experienced commercial clinical trial sites.

Treatment is administered at site and participants will receive study intervention directly from the investigator or designee, under medical supervision. The date and time of each dose administered in the clinic will be recorded in the source documents and captured in the eCRF. Deviation(s) from the trial-specific dosage regimen as given in section 4.7.2 are not permitted. Dates of intervention will also be recorded.

4.7.5. Assignment of trial subjects to treatment groups

According to section 4.7.5 of the accompanying master protocol:

Subject fulfilling selection criteria will be randomised to the different treatment arms in the trial through a central procedure. Randomisation will be stratified according to:

- Vaccine product used for primary vaccination (detailed in the concerned sub-protocol).
- Trial Site.
- Gender (female/male).
- Immune status (competent, immunocompromised as applicable in the concerned sub-protocol).

- Documented history of prior COVID-19 infection (none, asymptomatic, symptomatic/pre-vaccination or post-vaccination).

The participants are randomised into the study arms as defined in each sub-protocol. Randomisation will be implemented by a 24/7-Internet service (ALEA 17.1, FormsVision BV, Abcoude, NL) and prepared centrally by the Institute of Medical Statistics and Computational Biology (IMSB) at the University of Cologne.

Specific to this trial, Part B:

Subjects fulfilling selection criteria will be randomised to 4th dose through a central procedure.

Subjects will be randomised in a 1:1 ratio to one of the two treatment groups:

- 4th vaccination with BTN162b2 (Comirnaty®), including modified vaccine product.
- 4th vaccination with mRNA-1273 (Spikevax®), including modified vaccine product.

Randomisation will be stratified as described below:

Stratification is planned according to the pre-study vaccination series eligible for Part B (primary vaccination plus 3rd vaccine dose (= first booster), gender (female/male), documented history of prior COVID-19 infection (yes/no), as applicable and defined also by enrolment criteria.

In this trial, there is no stratification in the randomisation

- according to the status of immune competency of the trial subject.
- according to trial site.

4.7.6. Selection of dosage of investigational medicinal product

Treatment will be given as a single shot using the approved dose and mode of administration of each vaccine included in this trial.

4.7.6.1. Justification of the 0.5 ml (100 µg) booster dose of Moderna's Spikevax COVID-19 vaccine (mRNA-1273)

In the present *EU-COVAT-1_AGED* study, subjects aged 75 years or older receive a booster dose of 0.5 ml (100 µg) mRNA-1273. This investigational booster dose of mRNA-1273 is identical with the first and second mRNA-1273 dose administered in the primary vaccination series.^{22,23}

Under the jurisdictions of both FDA and EMA, mRNA-1273 is approved for a booster dose (3rd vaccination) of 0.25 ml (50 µg) six months after completion of the primary vaccination series in

individuals 18 years of age or older.^{22,23} An mRNA-1273 dose of 0.5 ml (100 µg) one month after the primary vaccination series is approved in severely immunocompromised individuals, such as after organ transplantation or at an equivalent level of immunocompromise.^{22,23}

The rationale for the lower booster dose of 0.25 ml (50 µg) was provided by Moderna, Inc. as follows:

"- Goal was to use optimal effective dose for boosting.

- Lower booster doses than those used for primary series of other vaccines [was] shown to reactivate immune memory.

- Lower booster dose increases worldwide vaccine supply of mRNA-1273."²⁴

Safety, especially with regard to a potential myocarditis risk of the booster, was not a driver in choosing the 0.25 ml (50 µg) booster dose instead of 0.5 ml (100 µg). However, myocarditis/ pericarditis is indeed a concern in individuals of male sex aged under 30 years receiving either of the currently approved mRNA COVID-19 vaccines. Surveillance studies showed that myocarditis reporting rates were 40.6 cases per million second doses of mRNA COVID-19 vaccines administered to males aged 12–29 years and 2.4 per million second doses administered to males aged ≥30 years; reporting rates among females in these age groups were 4.2 and 1.0 per million second doses, respectively.^{25,26} In comparison to the Pfizer/BioNTech BNT162b2 mRNA vaccine, there are 21.5 excess cases of myocarditis (including pericarditis) per million doses of the Moderna vaccine in males aged 18 to 39 years 0 to 7 days after the second dose²⁵. Accordingly, the FDA Fact Sheet provides the following information for mRNA-1273: "*Postmarketing data demonstrate increased risks of myocarditis and pericarditis, particularly within 7 days following the second dose. The observed risk is higher among males under 40 years of age than among females and older males. The observed risk is highest in males 18 through 24 years of age.*"²²

As outlined above, the target population of the present EUCOVAT-1_AGED study (75 years or older) does not fall into the at-risk group for an increased level of myocarditis/pericarditis after vaccination with mRNA-1273. Besides, there is further reassuring information available regarding the potential myocarditis/pericarditis risk of a booster dose (3rd dose) as compared to the second dose of an mRNA vaccine: "*Extrapolation from [Israeli surveillance] data obtained with the Pfizer-BioNTech COVID-19 vaccine [...] suggests that the risk of myocarditis for the Moderna COVID-19 Vaccine following a third dose several months following the primary vaccination series is not associated with an unacceptable risk of myocarditis/pericarditis. [...] ... the risk of myocarditis/pericarditis appears to be more similar after the administration of the third dose to the*

risk observed after the first dose."²⁷ Of note, vaccinees with the Pfizer/BioNTech vaccine BNT162b2 receive identical doses for the booster as for the first and second administrations²⁸.

With a booster dose of mRNA-1273 identical to the doses of the primary vaccination series very old individuals (> 75 years) with assumed immunosenescence²⁹ may thus benefit from increased immunogenicity while not being exposed to a currently detectable increased risk of myocarditis/pericarditis.

Meanwhile, Moderna Tx. has communicated data that demonstrate markedly increased levels of Omicron neutralizing antibodies after the 100 µg mRNA-1271 booster (3rd) dose as compared to the 50 µg dose³⁰.

A full booster (3rd) dose (0.5 ml, 100 µg) of mRNA-1273 was administered in two subgroups of the COV-BOOST trial, either following primary vaccination series with twice ChAdOx1-S or twice BNT162b2. The median age in the ChAdOx1-S subgroup (n=112) was 70.2 years and 65.0 years in the BNT162b2 group (n=111)³¹. Data on a full dose mRNA-1273 booster in the very old above 75 years of age is thus still missing.

4.7.7. Time of administration and adjustments to dosage of the investigational medicinal product in the individual trial subject

Not applicable.

4.7.8. Blinding

No blinding is foreseen in this trial.

4.7.8.1. Unblinding

Not applicable.

4.7.9. Previous and concomitant medication

According to section 4.7.8. of the accompanying master protocol:

There are no previous or concomitant medication prohibited in this protocol. Any medication at the time of enrolment or received during the study must be recorded along with:

- Reason for use.

- Date of administration including start and end dates.
- Dosage information including dose and frequency.

4.7.9.1. Rescue therapy for emergencies

For any adverse drug reaction that is deemed an emergency (e. g. severe allergic reactions), rescue therapy according to standard of care will be applied and the trial subject be followed up until full resolution of the adverse drug reaction.

4.7.10. Continuation of treatment after the end of the clinical trial

Not applicable.

4.8. Efficacy and safety endpoints

According to section 4.8 of the accompanying master protocol:

Main overarching immunogenicity variables to be included in the sub-protocols are those standard tests showing the immune response to SARS-CoV-2 vaccines, as described below.

Overarching safety variables of interest include unsolicited and solicited adverse events day 14, as applicable, after a 4th vaccination dose administration and severe adverse events for the duration of the trial.

Specific to Part B of this clinical trial:

This trial aims to evaluate immunogenicity and safety of a 4th vaccination dose of COVID-19 vaccines in older (≥ 75) subjects having received a primary vaccination series plus a 3rd vaccine dose > 1 month ago at the time of enrolment.

4.8.1. Measurement of efficacy and safety endpoints in Part B

4.8.1.1. Primary endpoints

According to section 4.8.1.1 of the accompanying master protocol:

- Rate of 2-fold antibody titre increase 14 days **after the 4th vaccination dose** measured by quantitative enzyme-linked immunosorbent assay (Anti-RBD-ELISA) against wild-type virus.

4.8.1.2. Safety endpoints

- Unsolicited AEs until the end of trial.

- Solicited AEs for 7 days after a 4th vaccination dose.
- Rate of severe adverse events (AEs) Grade ≥3 according to the National Cancer Institute Common Toxicity Criteria up to three months after a 4th vaccination dose (Note: Adverse events Grade ≥3 must be reported as SAE by using study specific SAE reporting process, see section 7.3).

4.8.1.3. Secondary endpoints

- Change in neutralizing antibody titre (Virus Neutralisation Assay) **against wild-type** 14 days after a 4th vaccination dose, to be determined in a subgroup only.
- Change in neutralizing antibody titre (Virus Neutralisation Assay) **against variants of concern** 14 days after a 4th vaccination dose, to be determined in a subgroup only.
- Antibody titre level **12 months** after a 4th vaccination dose measured by a quantitative enzyme-linked immunosorbent assay (anti-RBD-ELISA assay).
- Neutralizing antibody titre (Virus Neutralisation Assay) **against wild-type SARS-CoV-2** at 12 months after a 4th vaccination dose, to be determined in a subgroup only.
- Neutralizing antibody titre (Virus Neutralisation Assay) **against variants of concern** at 12 months after a 4th vaccination dose, to be determined in a subgroup only.

4.8.1.4. Exploratory endpoints

- Change in cellular immune response measured by qPCR 14 days after 4th booster dose, to be determined in a subgroup only.
- Neutralising capacity measured by neutralising activity against newly emerging variants in bio-banked samples after a 4th vaccination dose, to be determined in a subgroup only.
- Correlates of humoral immune response, cellular immune responses and viral neutralising capacity against SARS-CoV-2 variants of concern (VOCs), to be determined in a subgroup only.

Please note that the size of the above-mentioned subgroups (sections 4.8.1.3 and 4.8.1.4) is targeted to be 200 subjects each. Analysis will be performed in all samples if additional funding becomes available.

4.8.1.5. Safety data in Part B

- Solicited AEs (as defined in section 7.1.7) for 7 days after an on-trial 4th vaccination dose will be collected by using a diary (electronic or paper-based). Information collected will be entered into the eCRF by designated study site personnel.

- Unsolicited adverse events will be collected during visits up to the end of trial upon an open question by the investigator to the participant. Those unsolicited AEs graded as severe by the subject will be evaluated by the investigator to define the relationship with administered vaccines. Only those considered related will be accounted for and reported. Serious adverse events (SAEs) will be collected through an open question.
- SADRs will be collected and reported during the visits 3 to 5, reported spontaneously by the subject or elicited after an open question about any event of interest since the previous visit.

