7.1.3. Serious adverse events and serious adverse reactions

According to section 7.1.3. in the accompanying master protocol:

A serious AE (SAE) or serious ADR (SAR) is any untoward medical occurrence that at any dose:

1. Results in death;
2. Is life-threatening at the time of the event;
3. Requires inpatient hospitalisation or prolongation of existing hospitalisation;

4. Results in persistent or significant disability/incapacity;
5. Is a congenital anomaly or birth defect;
6. Is any other medical important event in the opinion of the investigator.

Additionally, those adverse events Grade ≥ 3 which are assessed as related to IMP by the investigator, will be reported as SAE by indicating “other medical important event” as seriousness criterion on the SAE report form and eCRF, if no other seriousness criteria apply.

Inpatient hospitalisation is defined as any stay in hospital that includes at least one night (midnight to 06:00). Admission to hospital as an inpatient planned before the first admission of the IMP is not considered as SAE but must be documented in a proper manner in the trial subject’s medical records and CRF (see Section 7.1.1).

EXCEPTIONS: the following events are not considered as SAE requiring immediate reporting to the sponsor:

- The participant is formally admitted to a hospital for medical reasons with no seriousness criterion and does not require overnight hospitalisation.
- Elective or previously scheduled surgery or medical treatment; hospitalisation for social or administrative reasons.
- Pre-existing diseases or present conditions detected prior to start of study drug administration and which do not worsen.

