7.2.2. Severity of the adverse event

According to section 7.2.2. in the accompanying master protocol:

The CTCAE (Common Terminology Criteria for Adverse Events) grading table (v5.0) will be used by trial investigators to classify adverse events. It comprises the following categories:

- Grade 1: Mild.
Asymptomatic or mild symptoms; clinical or diagnostic observations only; intervention not indicated.
- Grade 2: Moderate.
Minimal, local or non-invasive intervention indicated; limiting age-appropriate instrumental activities of daily living* (ADL).
- Grade 3: Severe or medically significant but not immediately life-threatening.

Hospitalization or prolongation of hospitalization indicated; disabling; limiting self-care ADL**.

- Grade 4: Life-threatening consequences.
Urgent intervention indicated.
- Grade 5: Death related to AE.
(Apart from grading methods each death is to be assessed as grade 5).

*Instrumental ADL refer to preparing meals, shopping for groceries or clothes, using the telephone, managing money etc.

**Self-care ADL refer to bathing, dressing and undressing, feeding self, using the toilet, taking medications, and not bedridden.

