7.2.3. Causal relationship between adverse event and investigational medicinal product

According to section 7.2.3 in the accompanying master protocol:

The investigator will assess therefore every AE whether a causal relationship with the IMP and/or study procedure can be assumed or not. The assessment includes consideration of the nature and type of reaction, the temporal relationship with the IMP, the clinical status of the trial subject, concomitant medication and other relevant clinical factors. If the event is considered as a symptom or sign of an underlying disorder, no causal relationship will be assumed.

Every AE will be assessed (eCRF/SAE-Report) according to the causality determinations of CIOMS VI-Group (Council for International Organizations of Medical Sciences) as follows:

- Related: There is a reasonable possibility that the AE may be related to the IMP.
- Not related: There is not a reasonable possibility that the AE may be related to the IMP.

A report on an event which cannot be judged because information is insufficient or contradictory or has not been judged will be regarded as related.

Specific to this trial:

The investigator will assess therefore every AE whether a causal relationship with the following IMPs and/or study procedure can be assumed or not.

IMP:

- BTN162b2 (Comirnaty).
- mRNA-1273 (Spikevax).

Vaccines can be modified in composition to address emerging VOCs.

Please follow the below clarifications from the master protocol for the assessment of relatedness.

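### The three-month Grade ≥3 safety endpoint has no single definition (serious or severe, all events or related only), so non-serious Grade 3 events judged unrelated are counted under some sections and not under others

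*Protocol*

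**What the plan says.** The third Part B safety endpoint is a rate of Grade ≥3 events up to three months after the fourth dose. Four sets of passages decide what enters its numerator.

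- **Endpoint wording.** The Protocol synopsis, Protocol 6.2, the SAP synopsis and SAP 10 count *serious* events (SAEs) of Grade ≥3. Protocol 4.8.1.2 and SAP 7 give instead "Rate of severe adverse events (AEs) Grade" ≥3, with no condition on seriousness or relationship. The overarching safety variables in Protocol 4.8 and SAP 7, taken from the master protocol, also name "severe adverse events for the duration of the trial".
- **Route to SAE status.** A note in Protocol 4.8.1.2 and SAP 7 says that Grade ≥3 events "must be reported as SAE by using study specific SAE reporting process". Protocol 7.1.3 lists the seriousness criteria and then adds only those Grade ≥3 events "which are assessed as related to IMP by the investigator, will be reported as SAE".
- **Relationship.** Protocol 4.8.1.5 and SAP 7 have the investigator assess causality for unsolicited events that the subject grades severe, and continue: "Only those considered related will be accounted for and reported". Protocol 7.2.1, by contrast, has every AE entered in the eCRF with its severity, causality and seriousness. Protocol 6.2 and SAP 10 plan listings that show related and unrelated events.
- **Who grades.** Protocol 7.2.2 says that the CTCAE "grading table (v5.0) will be used by trial investigators to classify adverse events". It describes Grade 3 as "Severe or medically significant but not immediately life-threatening".

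**The concern.** *Serious* and *severe* are different attributes. A Grade 3 event that limits self-care, for example, need not meet any seriousness criterion in Protocol 7.1.3. The note in Protocol 4.8.1.2 would make the two wordings equivalent by routing every Grade ≥3 event through SAE reporting. Protocol 7.1.3 undoes this by asking for a related judgement where no other seriousness criterion applies. The related-only sentence in Protocol 4.8.1.5 works in the same direction.

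Two programmers could therefore follow the documents faithfully and produce different Grade ≥3 rates. Under the narrower readings, whether a non-serious Grade 3 event counts depends on an attribution made by an investigator who knows which vaccine was given. Protocol 4.7.6.1 notes that data on the full-dose mRNA-1273 booster above 75 years are lacking, so an unambiguous severe-event rate is one of the more useful things this trial can report.

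**Working it through.** The documents state no rate, power or precision for this endpoint, so there is no figure of the plan's own to reproduce. The check is to classify unsolicited Grade ≥3 events by seriousness and relationship, and to apply each rule to each class.

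| Class of Grade ≥3 event | *Severe* wording (Protocol 4.8.1.2, SAP 7) | *Serious* wording with the Protocol 4.8.1.2 note | *Serious* wording with Protocol 7.1.3 | Related-only sentence (Protocol 4.8.1.5, SAP 7), SAEs collected separately |
|---|---|---|---|---|
| Serious, related | counted | counted | counted | counted |
| Serious, unrelated | counted | counted | counted | counted |
| Non-serious, related | counted | counted | counted | counted |
| Non-serious, unrelated | counted | counted | **not counted** | **not counted** |

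Only the last row changes. It consists in practice of Grade 3 events, because Grade 4 (life-threatening) and Grade 5 (death) correspond to seriousness criteria. Protocol 7.3, to which the note refers, requires every SAE to be reported but does not say which Grade ≥3 events become SAEs.

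**Scale.** Part B randomises 550 subjects 1:1, or 550/2 = 275 per arm. I assume all are vaccinated and so enter the safety population. One subject left out moves an arm's rate by 1/275 = 0.36 percentage points.

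**Illustration.** Let p be the share of subjects with any Grade ≥3 event. Let u be the share of those subjects whose only such events are non-serious and judged unrelated. The documents give neither, so both are assumptions.

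- Subjects left out = 275 × p × u
- Rate reported under a narrow reading = p × (1 − u)

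For p = 5%, 275 × 0.05 = 13.75 subjects have an event. The number left out is 1.4, 3.4 or 5.5 for u = 10%, 25% or 40%.

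| p | u = 10% | u = 25% | u = 40% |
|---|---|---|---|
| 3% | 2.7% | 2.25% | 1.8% |
| 5% | 4.5% | 3.75% | 3.0% |
| 10% | 9.0% | 7.5% | 6.0% |

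For comparison, the exact (Clopper-Pearson) 95% interval for 14/275 = 5.1% runs from 2.8% to 8.4%. At p = 5% the shift of 0.5 to 2.0 points lies within one arm's sampling error. Unlike sampling error, it goes in one direction relative to the all-cause rate and does not shrink with more subjects.

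**The case against.** The related-only sentence does not name the three-month endpoint, and it concerns events graded severe by the subject, whereas the endpoint uses CTCAE grades assigned by investigators. It may mean onward safety reporting only. Protocol 7.2.1 and the planned related/unrelated listings favour that reading. This is fair as far as data capture goes, but the text does not say so, and the sentence is repeated in the SAP, where it reads as a counting rule. Even on the benign reading, the *serious*/*severe* conflict and the conflict between Protocol 4.8.1.2 and 7.1.3 remain.

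Grade 3 also overlaps with seriousness: hospitalisation and disability appear in both definitions, and the investigator may call any event medically important. This shrinks the affected class but does not empty it, and it makes inclusion discretionary.

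Four of the six endpoint statements, including both analysis sections, say *serious*. If that is the intended endpoint, leaving out non-serious unrelated events is correct rather than biased. This stands: a rate is understated only relative to the all-cause *severe* wording. It does not remove the need to say which is meant.

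The consequences are limited. SAEs are reported whatever their relationship, solicited diary events fall outside the related-only sentence, and under Protocol 7.2.3 an event that cannot be judged or "has not been judged will be regarded as related". The safety analysis is descriptive, no decision rule in these documents uses this endpoint, and nothing shows that attribution differs between the vaccines. All of this stands.

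**Conclusion.** The concern holds. The current text defines a listed safety endpoint in incompatible ways, in both documents and within the SAP itself, and does not rank the definitions. The effect is confined to non-serious Grade 3 events judged unrelated. Its size cannot be computed from the documents; only the 0.36 points per subject follows from the planned numbers, on the assumption that all 275 per arm are vaccinated. The 3%, 5% and 10% event rates and the values of u are illustrative. This should be settled before the safety tables are produced, but it does not touch the immunogenicity analyses.

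**What to change.** Use one wording in both synopses, Protocol 4.8.1.2 and 6.2, and SAP 7 and 10. I suggest: subjects with at least one AE of CTCAE v5.0 Grade ≥3, as graded by the investigator, within three months of the fourth dose, regardless of relationship, by arm. Show SAEs and related Grade ≥3 events as separate rows. This follows the existing *severe* wording.

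Three further edits are needed:

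- Delete the related-only sentence from Protocol 4.8.1.5 and SAP 7, or limit it expressly to onward safety reporting, so that it restricts neither recording nor tabulation.
- Reconcile the note in Protocol 4.8.1.2 and SAP 7 with Protocol 7.1.3 on which Grade ≥3 events go through SAE reporting.
- State that the subject's grading prompts evaluation, while the grade analysed is the investigator's.

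The cost is rewording and some additional events to list and tabulate. If sites followed Protocol 7.2.1, the eCRF already holds severity, causality and seriousness for every AE and no new data are needed. If a site treated the related-only sentence as a recording rule, rewording will not recover the missing events and that site's records would have to be checked.
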